8.3. Clinical Laboratory Tests

8.3.1. Laboratory Value Definitions

All laboratory assessments will be performed using a central laboratory except for urine pregnancy tests (as applicable). Laboratory values and change from baseline values will be summarized descriptively by visit, and non-numeric test values will be tabulated when necessary.

The baseline value will be determined using the last nonmissing value collected before the first application, prioritizing scheduled assessments for baseline identification over unscheduled visits. The last record before administration in the highest priority will be considered the baseline record. For baseline laboratory candidates with the same date and time in the same priority category, additional rules may be provided after consultation with the medical monitor to delineate which value will be defined as baseline.

8.3.2. Laboratory Value Summaries

Clinical laboratory tests, including hematology and serum chemistry, will be performed at the Protocol-specified visits. If specific safety issues arise, additional unscheduled laboratory tests/analyses may be performed at the discretion of the investigator.

All test results and associated normal ranges from central laboratories will be reported in SI units. All tests with numeric values will have a unique unit per test. Any laboratory test results and associated normal ranges from local laboratories will be converted to SI units.

When there are multiple laboratory nonmissing values for a participant's particular test within a visit window, the laboratory value with the smallest laboratory sequence number will be used in by-visit summaries.

For test results that will be summarized with available normal ranges, the number and percentage of participants with the laboratory values being low (but never high), normal, high (but never low), and both low and high will be calculated for each test. This shift summary will be produced for each test for the safety population in VC period. Shift tables will be presented showing change in CTCAE grade from baseline to worst grade postbaseline as well. The denominator for the percentage calculation will use the number of participants in the baseline category.

Subgroup analysis for laboratory results by age categories will also be provided.

8.4. Vital Signs

Values at each scheduled visit, change, and percentage change from baseline for vital signs, including SBP, DBP, pulse, respiratory rate, and body temperature will be summarized descriptively.

Criteria for clinically notable vital sign abnormalities are defined in [Table 3](#), [Table 4](#), and [Table 5](#). The abnormal values for participants exhibiting clinically notable vital sign abnormalities will be listed along with their assigned treatment group. Alert vital signs are defined as an absolute value outside the defined range and percentage change greater than 25%. The abnormal values for participants exhibiting alert vital sign abnormalities will be listed.

Table 3: Criteria for Clinically Notable Vital Sign Abnormalities for 12 to 15 Years Old

Parameter	High Threshold	Low Threshold
Systolic blood pressure	> 131 mmHg	< 110 mmHg
Diastolic blood pressure	> 83 mmHg	< 64 mmHg
Pulse	> 100 bpm	< 60 bpm
Temperature	> 38.0°C	< 35.5°C
Respiratory rate	> 20 breaths/min	< 8 breaths/min

Table 4: Criteria for Clinically Notable Vital Sign Abnormalities for 16 to 17 Years Old

Parameter	High Threshold	Low Threshold
Systolic blood pressure	> 120 mmHg	< 90 mmHg
Diastolic blood pressure	> 85 mmHg	< 50 mmHg
Pulse	> 100 bpm	< 45 bpm
Temperature	> 38.0°C	< 35.5°C
Respiratory rate	> 20 breaths/min	< 8 breaths/min

Table 5: Criteria for Clinically Notable Vital Sign Abnormalities for ≥ 18 Years Old

Parameter	High Threshold	Low Threshold
Systolic blood pressure	> 155 mmHg	< 85 mmHg
Diastolic blood pressure	> 100 mmHg	< 40 mmHg
Pulse	> 100 bpm	< 45 bpm
Temperature	> 38°C	< 35.5°C
Respiratory rate	> 20 breaths/min	< 8 breaths/min

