2.4. Benefit/Risk Assessment

Ruxolitinib presents a low risk of cutaneous toxicity both in animals and clinical studies. Ruxolitinib cream tested positive in a photoclastogenicity assay; hence, there may be a risk of skin reaction to the combined exposure of ruxolitinib and sunlight. Ruxolitinib cream did not act as a contact sensitizer nor did it produce significant dermal irritation or demonstrate phototoxicity or photoallergenic potential. This lack of adverse cutaneous effects has been supported by clinical studies to date, where cutaneous AEs have been infrequent and of similar frequency and severity as with vehicle control treatment. Participants should be cautioned to avoid excessive exposure to either natural or artificial sunlight (including tanning booths, sun lamps, etc).

The primary clinical risks noted with orally administered ruxolitinib treatment for polycythemia vera or myelofibrosis are the potential sequelae of decreased hematopoietic proliferation secondary to the inhibition of growth factor pathways by JAK2 antagonism. Dose-dependent, reversible thrombocytopenia has been observed in participants with myelofibrosis, as well as anemia and less frequently neutropenia. An increased rate of infection is an additional potential risk of immunomodulation. In healthy participants and rheumatoid arthritis participants with greater bone marrow reserve, the effects on hematopoietic proliferation appear to be less pronounced. Ruxolitinib cream has [REDACTED] of the relative systemic availability of oral treatment, which was studied in participants with psoriasis. Owing to its low systemic bioavailability, ruxolitinib cream is not expected to bring about clinically significant changes in hematology laboratory investigations.

The results of the INCB 18424-206 dose range-finding study in adults with AD are provided and discussed in more detail in Section 2.2.2.4.1. The efficacy outcomes for all treatment groups can be summarized as follows:

- IGA response and EASI50/75/90 response rates showed all ruxolitinib cream treatment regimens to be efficacious and statistically superior to its vehicle.
- Efficacy was time- and regimen-related, with 1.5% cream QD and 1.5% cream BID numerically greater than the other treatment groups, including the active control (TC 0.1% cream BID).
- All ruxolitinib cream strengths continued to demonstrate improvement through Week 8.

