8.3.3. Vital Signs

Vital sign measurements (to be taken before blood collection for laboratory tests), include blood pressure, pulse, respiratory rate, and body temperature. Blood pressure and pulse will be taken with the participant in the sitting position after 5 minutes of rest. Height and weight will also be assessed at screening, Weeks 8, 24 and 52/EOT. Abnormal vital sign results identified after the first dose of study treatment constitute an AE if they are considered clinically meaningful, induce clinical signs or symptoms, or require concomitant therapy.

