1. INTRODUCTION

INCB 18424-303 is a randomized, vehicle-controlled study in adolescent and adult (≥ 12 years old) participants with AD eligible for topical therapy. Approximately 600 participants will be randomized 2:2:1 to ruxolitinib 0.75% cream BID, ruxolitinib 1.5% cream BID, or vehicle cream. In addition, approximately 20% of the overall study population will consist of adolescents. Participants with baseline IGA score of 2 will constitute up to approximately 25% of the overall study population. Participants with AD involvement of 3% to 20% BSA and IGA score of 2 to 3 will receive blinded study treatment for 8 weeks followed by a randomized 44-week LTS extension period. In the LTS period, participants initially randomized to vehicle will receive either ruxolitinib 0.75% or 1.5% cream BID.

The purpose of this SAP is to provide details of the statistical analyses that have been outlined in the study Protocol. The scope of this plan will be executed by the Department of Biostatistics or designee, and the analyses of PK will be executed by the Department of Clinical Pharmacokinetics or designee.

Another Phase 3 study, INCB 18424-304, has the identical study design as INCB 18424-303. This SAP applies to both INCB 18424-303 and INCB 18424-304 studies.

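### SAP 8.4: the temperature alert cannot be met as defined, and the notable blood-pressure limits are inconsistent across age bands with no stated rationale

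*SAP*

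**What the plan says.** SAP 8.4 sets two levels of flag for vital signs.

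- **Clinically notable.** A value is notable if it crosses the limits in Table 3 (12 to 15 years), Table 4 (16 to 17 years) or Table 5 (18 years and over). There is no condition on change from baseline. The output is a listing: "The abnormal values for participants exhibiting clinically notable vital sign abnormalities will be listed along with their assigned treatment group".
- **Alert.** The rule is the same for every parameter: "Alert vital signs are defined as an absolute value outside the defined range and percentage change greater than 25" percent. Alert values are listed as well.

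Temperature limits (below 35.5°C, above 38.0°C), respiratory-rate limits and the high pulse limit are the same in all three tables. The systolic, diastolic and low pulse limits differ by age band. The section gives no source for any limit and no rule for assigning the age band.

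On the affected group, SAP 1 says that "approximately 20% of the overall study population will consist of adolescents", and that the same SAP governs study INCB 18424-304. On infection, Protocol 2.4 states: "An increased rate of infection is an additional potential risk of immunomodulation".

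**The concern.** A percentage-change condition suits quantities whose ordinary variation is a sizeable share of their level. Body temperature in Celsius varies by a few degrees around 37, so a 25% change lies outside any plausible reading. An alert category that cannot be reached gives a listing that is empty by construction, and a reader of the study report could take the empty listing as reassurance.

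Separately, one would expect age-specific limits to move in a consistent direction with age, or to come with a reason where they do not. Here the systolic high limit falls and then rises, and the low limits drop sharply between 15 and 16. The notable listing depends on the limit alone, so the same reading is listed or not according to which side of a birthday the participant is assigned. At stake is how far the vital-sign listings can be interpreted for adolescents, about 20% of about 600 participants (0.20 × 600 = 120), in a study whose extension exists to collect safety data.

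**Working it through.** The plan gives no derived figure to reproduce here. Both parts are direct checks on SAP 8.4.

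**1. Temperature alert**

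Inputs: limits of 35.5 and 38.0°C, and a required change above 25%, read as change from baseline because that is the change SAP 8.4 summarises. For baseline *b*:

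- high alert: reading > max(38.0, 1.25*b*)
- low alert: reading < min(35.5, 0.75*b*)

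| Baseline (°C) | High alert needs more than | Low alert needs less than |
|---|---|---|
| 35.5 | 44.4 | 26.6 |
| 36.5 | 45.6 | 27.4 |
| 37.0 | 46.3 | 27.8 |
| 38.0 | 47.5 | 28.5 |

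In reverse, a reading just above 38.0°C would count as a 25% rise only from a baseline below 38.0 / 1.25 = 30.4°C. A reading just below 35.5°C would count as a 25% fall only from a baseline above 35.5 / 0.75 = 47.3°C. Computing the percentage in Fahrenheit moves the limits further out: from 35.5°C (95.9°F) the high alert needs 119.9°F, or 48.8°C.

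**2. Notable limits by age band**

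| Limit | 12–15 (Table 3) | 16–17 (Table 4) | 18+ (Table 5) |
|---|---|---|---|
| Systolic high, mmHg | > 131 | > 120 | > 155 |
| Systolic low, mmHg | < 110 | < 90 | < 85 |
| Systolic width not flagged | 131 − 110 = 21 | 120 − 90 = 30 | 155 − 85 = 70 |
| Diastolic high, mmHg | > 83 | > 85 | > 100 |
| Diastolic low, mmHg | < 64 | < 50 | < 40 |
| Pulse low, bpm | < 60 | < 45 | < 45 |

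Classifying whole-number readings against the tables:

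- Systolic 121 to 131 is flagged high only at 16 to 17, so 125 is unflagged at 15, flagged at 16 and unflagged at 18.
- Systolic 90 to 109 and diastolic 50 to 63 are flagged low only at 12 to 15. A reading of 108/62 is therefore flagged on both values at 15 and on neither at 16.
- Diastolic 84 to 85 (high) and pulse 45 to 59 (low) are flagged only at 12 to 15.

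**3. How full the notable listing might be (assumption only)**

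The documents give no blood-pressure distribution for adolescents, so this is an illustration. With normal readings, the share flagged is Φ((low − mean)/SD) + 1 − Φ((high − mean)/SD). For an assumed systolic mean of 110 and SD of 10:

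- 12–15: Φ(0) + 1 − Φ(2.1) = 0.500 + 0.018 = 0.518
- 16–17: Φ(−2) + 1 − Φ(1) = 0.023 + 0.159, about 0.18
- adult limits: about 0.006

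| Assumed range | 12–15 limits | 16–17 limits | Adult limits |
|---|---|---|---|
| Systolic mean 105–120, SD 8–12 | 19% to 74% | 6% to 51% | under 5% |
| Diastolic mean 60–75, SD 7–9 | 19% to 72% | 2% to 14% | under 2% |

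The range is wide. At an assumed systolic mean of 120 the 16–17 limits flag more readings than the 12–15 limits (about 50% against 19% to 38%), so even which band is over-flagged depends on the assumption. The share of participants flagged at least once also depends on within-person correlation and is not estimated here.

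The systolic alert behaves differently. With the same assumed means and SDs and an assumed correlation of 0.5 between baseline and later reading, simulation puts it at about 0.02% to 2% of readings against the adolescent limits.

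**The case against.** The strongest reply is that nothing important rests on these flags. No efficacy endpoint, analysis population or adverse-event definition uses them. Under Protocol 8.3.3, "Abnormal vital sign results identified after the first dose of study treatment constitute an AE if they are considered clinically meaningful", or if they cause signs or symptoms or need concomitant therapy, and that is the investigator's judgement. Values and changes from baseline are still summarised at each visit. This stands, and it keeps the point minor. It does not rescue a rule that cannot be met or limits that reverse without explanation.

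Several stronger readings are tempting and are not supported:

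- **That the tables contradict each other.** They cover separate ages, so no reading falls under two rules. The fault is unexplained inconsistency between bands.
- **That the alert rule fills the listings with ordinary values.** The 25% condition does the opposite: an alert that cannot fire adds no rows. Any over-flagging concerns only the notable listing, and its size cannot be derived from the documents.
- **That a real blood-pressure change in adolescents would be hidden.** The by-visit summaries and dedicated systolic and diastolic tables remain, and clinically meaningful values become adverse events, which are tabulated by age group.
- **That fever would be missed.** Any reading above 38.0°C is listed as notable. The infection sentence in Protocol 2.4 also sits in a discussion of oral treatment, which goes on to stress the cream's low systemic exposure.
- **That participants change status at a birthday.** The SAP does not say that age is updated. Protocol 8.1.5.1 collects it at screening and SAP 6.1.1 treats age group as a demographic, so a fixed band is a natural reading. But participation lasts up to 60 weeks (Protocol 4.2), and Protocol 5.1 expects some adolescents to reach adulthood on study, so the rule should be written down.

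**Conclusion.** SAP 8.4 is wrong as written in two respects, both minor, and both established from the document alone.

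First, the temperature alert is inoperative: it would need a reading above about 44°C or below about 28.5°C from any baseline of 35.5 to 38.0°C. The only assumption is that the percentage is taken from baseline.

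Second, the notable blood-pressure limits are inconsistent across ages 12–15, 16–17 and 18+, and the low pulse limit steps from 60 to 45 bpm at age 16. No rationale is given, and the rule for assigning the band is not stated.

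The notable listing at 12 to 15 could contain a large share of ordinary readings, but that depends on assumed distributions and is not a finding from the documents. The number of participants affected is also unknown, since the split of the roughly 120 adolescents between the two bands is not given. The consequence is confined to descriptive safety listings, in this study and in INCB 18424-304.

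**What to change.** - Define the temperature alert by an absolute value or an absolute change in degrees, not by a percentage.
- Reconcile the blood-pressure and pulse limits in SAP Tables 3 and 4 against one stated source, checking them against Table 5, or give the reason for the differences. No limits are proposed here.
- State that each participant's age band is fixed at baseline.

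The cost is an edit to SAP 8.4 and reprogramming of the flags, made once for both studies. No new data are needed.

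Two further changes are optional preferences: requiring a notable value to be new relative to baseline, and tabulating the number and percentage of participants flagged by treatment and age group alongside the listings.

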9. PLANNED ANALYSES

No formal interim analysis is planned. There are 3 formal planned analyses:

- The primary analysis will occur after the primary database lock, when all participants have completed the vehicle-controlled, double-blind treatment period. The sponsor will be unblinded after the primary database lock; however, investigators and participants will remain blinded to the individual study treatment assignment;
- An analysis will occur when approximately 200 participants ($\geq 20\%$ adolescents) complete 12 months of treatment across both INCB 18424-303 and INCB 18424-304 studies;
- The final analysis will occur when all participants have completed or withdrew from the study.

10. CHANGES AND MODIFICATIONS TO THE ANALYSIS PLAN

All versions of the SAP are listed in [Table 6](#).

Table 6: Statistical Analysis Plan Versions

SAP Version	Date
Original	08 NOV 2019

10.1. Changes to Protocol-Defined Analyses

- The LTS evaluable population will not be used. Efficacy and safety in LTS will be evaluated in the ITT and safety populations to keep consistency with the measurements in VC.
- Duration of AEs will not be analyzed.
- The sleep-related impairment is considered as an important endpoint. The proportion of participants with a clinically meaningful improvement (≥ 6 -point) in the PROMIS Short Form – Sleep-Related Impairment (8a-24-hour recall) score at Weeks 8 has been moved into the list of key secondary endpoints with alpha control.

10.2. Changes to the Statistical Analysis Plan

Not applicable.

APPENDIX A. PLANNED TABLES AND FIGURES

This appendix provides a list of the planned tables, figures, and listing for the clinical study report. Standard tables will follow the conventions in the Standard Safety Tables initial version. Shells are provided for nonstandard tables. In-text tables are identical in structure and content as appendix tables, but follow a Rich Text Format.

The list of tables, figures, listings, and the shells are to be used as guideline. Modifications of the list or shells that do not otherwise affect the nature of the analysis will not warrant an amendment to the SAP.

Tables

Table No.	Title	Population
Baseline Demographic and Characteristic		
1.1.1	Analysis Populations	All
1.1.2	Summary of Participant Disposition	ITT
1.1.3	Summary of Number of Participants Enrolled by Country and Site	ITT
1.1.4	Summary of Protocol Deviations	ITT
1.2	Summary of Demographics and Baseline Characteristics	ITT
1.3	Summary of Baseline Disease Characteristics	ITT
1.4.1	Summary of Prior Medications	ITT
1.4.2	Summary of Prior Medications for Atopic Dermatitis	ITT
1.4.3.1	Summary of Concomitant Medications in VC Period	ITT
1.4.3.2	Summary of Concomitant Medications from Baseline to Week 52	ITT
1.4.3.3	Summary of Concomitant Medications in LTS Period	ITT
1.5	Summary of General Medical History	ITT
Efficacy		
IGA		
2.1.1.1	Summary and Analysis of Participants Achieving IGA-TS From Baseline to Week 52	ITT
2.1.1.2	Summary of Participants Achieving IGA-TS in LTS Period	ITT
2.1.2	Summary and Sensitivity Analysis of Participants Achieving IGA-TS at Week 8 by Tipping Point Analysis	ITT
2.1.3.1	Summary and Analysis of Participants Achieving IGA-TS From Baseline to Week 52	PP
2.1.4	Summary and Analysis of Participants Achieving IGA-TS by Baseline IGA Score From Baseline to Week 52	ITT
2.1.5	Summary and Analysis of Participants Achieving IGA-TS by Baseline EASI Score From Baseline to Week 52	ITT
2.1.6	Summary and Analysis of Participants Achieving IGA-TS by Region From Baseline to Week 52	ITT
2.1.7	Summary and Analysis of Participants Achieving IGA-TS by Age Group From Baseline to Week 52	ITT
2.1.8	Summary and Analysis of Participants Achieving IGA-TS by Sex From Baseline to Week 52	ITT
2.1.9	Summary and Analysis of Participants Achieving IGA-TS by Race From Baseline to Week 52	ITT

Table No.	Title	Population
2.1.10.1	Summary of Participants in Each Category of IGA Score From Baseline to Week 52	ITT
2.1.10.2	Summary of Participants in Each Category of IGA Score in LTS Period	ITT
2.1.11.1	Summary and Analysis of Participants Achieving an IGA of 0 or 1 From Baseline to Week 52	ITT
2.1.11.2	Summary of Participants Achieving an IGA of 0 or 1 in LTS Period	ITT
2.1.12	Shift Summary of IGA at Week 8	ITT
EASI		
2.2.1	Summary and Analysis of Participants Achieving EASI75 in VC Period	ITT
2.2.2	Summary and Analysis of Participants Achieving EASI50 in VC Period	ITT
2.2.3	Summary and Analysis of Participants Achieving EASI90 in VC Period	ITT
2.2.4	Summary and Analysis of EASI Score in VC Period	ITT
2.2.5	Summary of Participants in Each Category of EASI Score in VC Period	ITT
Itch NRS Score		
2.3.1	Summary and Analysis of Participants Achieving \geq 2-Point Improvement in Itch NRS Score in VC Period	ITT
2.3.2	Summary and Analysis of Participants With a \geq 3-Point Improvement in Itch NRS Score in VC Period	ITT
2.3.3	Summary and Analysis of Participants With a \geq 4-Point Improvement in Itch NRS Score in VC Period	ITT
2.3.4	Summary and Analysis of Itch NRS Score in VC Period	ITT
2.3.5	Summary and Analysis of Daily Itch NRS Score in VC Period	ITT
2.3.6	Summary and Analysis of Time to \geq 2-Point Improvement in Itch NRS Score in VC Period	ITT
2.3.7	Summary and Analysis of Time to \geq 3-Point Improvement in Itch NRS Score in VC Period	ITT
2.3.8	Summary and Analysis of Time to \geq 4-Point Improvement in Itch NRS Score in VC Period	ITT
PROMIS Sleep Disturbance Score (8b)		
2.4.1.1	Summary and Analysis of Participants Achieving a \geq 6-point Improvement in the PROMIS Sleep Disturbance Score (8b) From Baseline to Week 52	ITT
2.4.1.2	Summary of Participants Achieving a \geq 6-point Improvement in the PROMIS Sleep Disturbance Score (8b) in LTS Period	ITT
2.4.2.1	Summary and Analysis of By-Visit PROMIS Sleep Disturbance Score (8b) From Baseline to Week 52	ITT
2.4.2.2	Summary of By-Visit PROMIS Sleep Disturbance Score (8b) in LTS Period	ITT
2.4.3	Summary and Analysis of Daily PROMIS Sleep Disturbance Score (8b) in VC Period	ITT
PROMIS Sleep-Related Impairment Score (8a)		
2.5.1.1	Summary and Analysis of Participants Achieving a \geq 6-point Improvement in the PROMIS Sleep-Related Impairment Score (8a) From Baseline to Week 52	ITT
2.5.1.2	Summary of Participants Achieving a \geq 6-point Improvement in the PROMIS Sleep-Related Impairment Score (8a) in LTS Period	ITT
2.5.2.1	Summary and Analysis of By-Visit PROMIS Sleep-Related Impairment Score (8a) From Baseline to Week 52	ITT

Table No.	Title	Population
2.5.2.2	Summary of By-Visit PROMIS Sleep-Related Impairment Score (8a) in LTS Period	ITT
2.5.3	Summary and Analysis of Daily PROMIS Sleep-Related Impairment Score (8a) in VC Period	ITT
SCORAD		
2.6	Summary and Analysis of SCORAD Score in VC Period	ITT
Skin Pain NRS Score		
2.7.1	Summary and Analysis of By-Visit Skin Pain NRS Score in VC Period	ITT
2.7.2	Summary and Analysis of Daily Skin Pain NRS Score in VC Period	ITT
BSA		
2.8.1.1	Summary and Analysis of Total %BSA Afflicted by AD From Baseline to Week 52	ITT
2.8.1.2	Summary of Total %BSA Afflicted by AD in LTS Period	ITT
POEM		
2.9.1.1	Summary and Analysis of Total POEM Score From Baseline to Week 52	ITT
2.9.1.2	Summary of Total POEM Score in LTS Period	ITT
2.9.2.1	Summary of Participants in Each Category of POEM Score From Baseline to Week 52	ITT
2.9.2.2	Summary of Participants in Each Category of POEM Score in LTS Period	ITT
DLQI/CDLQI		
2.10.1.1	Summary and Analysis of Total DLQI Score From Baseline to Week 52	ITT
2.10.1.2	Summary and Analysis of Total CDLQI Score From Baseline to Week 52	ITT
2.10.1.3	Summary of Total DLQI Score in LTS Period	ITT
2.10.1.4	Summary of Total CDLQI Score in LTS Period	ITT
2.10.2.1	Summary and Analysis of DLQI Subscore From Baseline to Week 52	ITT
2.10.2.2	Summary and Analysis of CDLQI Subscore From Baseline to Week 52	ITT
2.10.2.3	Summary of DLQI Subscore in LTS Period	ITT
2.10.2.4	Summary of CDLQI Subscore in LTS Period	ITT
2.10.3.1	Summary of Participants in Each Category of DLQI Score From Baseline to Week 52	ITT
2.10.3.2	Summary of Participants in Each Category of CDLQI Score From Baseline to Week 52	ITT
2.10.3.3	Summary of Participants in Each Category of DLQI Score in LTS Period	ITT
2.10.3.4	Summary of Participants in Each Category of CDLQI Score in LTS Period	ITT
2.10.4.1	Summary and Analysis of Participants Achieving ≥ 4 Improvement in DLQI Score From Baseline to Week 52	ITT
2.10.4.2	Summary and Analysis of Participants Achieving ≥ 4 Improvement in CDLQI Score From Baseline to Week 52	ITT
2.10.4.3	Summary of Participants Achieving ≥ 4 Improvement in DLQI Score in LTS Period	ITT
2.10.4.4	Summary of Participants Achieving ≥ 4 Improvement in CDLQI Score in LTS Period	ITT
PGIC		
2.11.1	Summary and Analysis of Participants Achieving a PGIC Score of 1 or 2 in VC Period	ITT
2.11.2	Summary of Participants in Each Category of PGIC Score in VC Period	ITT
2.11.3	Summary of PGIC Score in VC Period	ITT

Table No.	Title	Population
EQ-5D-5L		
2.12.1	Summary and Analysis of EQ VAS Score From Baseline to Week 52	ITT
2.12.2	Summary of EQ VAS Score in LTS Period	ITT
WPAI-SHP		
2.13.1.1	Summary and Analysis of WPAI-SHP v2.0 Score From Baseline to Week 52	ITT
2.13.1.2	Summary of WPAI-SHP v2.0 Score in LTS Period	ITT
Exposure, Adverse Events, Laboratory, and Vital Signs		
Exposure		
3.1.1.1	Summary of Exposure in VC Period	Safety
3.1.1.2	Summary of Exposure From Baseline to Week 52	Safety
3.1.1.3	Summary of Exposure in LTS Period	Safety
3.1.2	Summary of Study Drug Compliance in VC Period	Safety
Adverse Events		
3.2.1.1	Overall Summary of Treatment-Emergent Adverse Events in VC Period	Safety
3.2.1.1.1	Overall Summary of Treatment-Emergent Adverse Events by Age Group in VC Period	Safety
3.2.1.2	Overall Summary of Treatment-Emergent Adverse Events From Baseline to Week 52	Safety
3.2.1.2.1	Overall Summary of Treatment-Emergent Adverse Events by Age Group From Baseline to Week 52	Safety
3.2.1.3	Overall Summary of Treatment-Emergent Adverse Events in LTS Period	Safety
3.2.2.1	Summary of Treatment-Emergent Adverse Events by MedDRA System Organ Class and Preferred Term in VC Period	Safety
3.2.2.1.1	Summary of Treatment-Emergent Adverse Events by MedDRA System Organ Class and Preferred Term by Age Group in VC Period	Safety
3.2.2.2	Summary of Treatment-Emergent Adverse Events by MedDRA System Organ Class and Preferred Term From Baseline to Week 52	Safety
3.2.2.2.1	Summary of Treatment-Emergent Adverse Events by MedDRA System Organ Class and Preferred Term by Age Group From Baseline to Week 52	Safety
3.2.2.3	Summary of Treatment-Emergent Adverse Events by MedDRA System Organ Class and Preferred Term in LTS Period	Safety
3.2.3.1	Summary of Treatment-Emergent Adverse Events by MedDRA Preferred Term in Decreasing Order of Frequency in VC Period	Safety
3.2.3.1.1	Summary of Treatment-Emergent Adverse Events by MedDRA Preferred Term in Decreasing Order of Frequency by Age Group in VC Period	Safety
3.2.3.2	Summary of Treatment-Emergent Adverse Events by MedDRA Preferred Term in Decreasing Order of Frequency From Baseline to Week 52	Safety
3.2.3.2.1	Summary of Treatment-Emergent Adverse Events by MedDRA Preferred Term in Decreasing Order of Frequency by Age Group From Baseline to Week 52	Safety
3.2.3.3	Summary of Treatment-Emergent Adverse Events by MedDRA Preferred Term in Decreasing Order of Frequency in LTS Period	Safety

Table No.	Title	Population
3.2.6.1	Summary of Grade 3 or Higher Treatment-Emergent Adverse Events by MedDRA System Organ Class and Preferred Term in VC Period	Safety
3.2.6.1.1	Summary of Grade 3 or Higher Treatment-Emergent Adverse Events by MedDRA System Organ Class and Preferred Term by Age Group in VC Period	Safety
3.2.6.2	Summary of Grade 3 or Higher Treatment-Emergent Adverse Events by MedDRA System Organ Class and Preferred Term From Baseline to Week 52	Safety
3.2.6.2.1	Summary of Grade 3 or Higher Treatment-Emergent Adverse Events by MedDRA System Organ Class and Preferred Term by Age Group From Baseline to Week 52	Safety
3.2.6.3	Summary of Grade 3 or Higher Treatment-Emergent Adverse Events by MedDRA System Organ Class and Preferred Term in LTS Period	Safety
3.2.7.1	Summary of Grade 3 or Higher Treatment-Emergent Adverse Events by MedDRA Preferred Term in Decreasing Order of Frequency in VC Period	Safety
3.2.7.1.1	Summary of Grade 3 or Higher Treatment-Emergent Adverse Events by MedDRA Preferred Term in Decreasing Order of Frequency by Age Group in VC Period	Safety
3.2.7.2	Summary of Grade 3 or Higher Treatment-Emergent Adverse Events by MedDRA Preferred Term in Decreasing Order of Frequency From Baseline to Week 52	Safety
3.2.7.2.1	Summary of Grade 3 or Higher Treatment-Emergent Adverse Events by MedDRA Preferred Term in Decreasing Order of Frequency by Age Group From Baseline to Week 52	Safety
3.2.7.3	Summary of Grade 3 or Higher Treatment-Emergent Adverse Events by MedDRA Preferred Term in Decreasing Order of Frequency in LTS Period	Safety
3.2.8.1	Summary of Serious Treatment-Emergent Adverse Events by MedDRA System Organ Class and Preferred Term in VC Period	Safety
3.2.8.1.1	Summary of Serious Treatment-Emergent Adverse Events by MedDRA System Organ Class and Preferred Term by Age Group in VC Period	Safety
3.2.8.2	Summary of Serious Treatment-Emergent Adverse Events by MedDRA System Organ Class and Preferred Term From Baseline to Week 52	Safety
3.2.8.2.1	Summary of Serious Treatment-Emergent Adverse Events by MedDRA System Organ Class and Preferred Term by Age Group From Baseline to Week 52	Safety
3.2.8.3	Summary of Serious Treatment-Emergent Adverse Events by MedDRA System Organ Class and Preferred Term in LTS Period	Safety
3.2.9.1	Summary of Serious Treatment-Emergent Adverse Events by MedDRA Preferred Term in Decreasing Order of Frequency in VC Period	Safety
3.2.9.1.1	Summary of Serious Treatment-Emergent Adverse Events by MedDRA Preferred Term in Decreasing Order of Frequency by Age Group in VC Period	Safety
3.2.9.2	Summary of Serious Treatment-Emergent Adverse Events by MedDRA Preferred Term in Decreasing Order of Frequency From Baseline to Week 52	Safety
3.2.9.2.1	Summary of Serious Treatment-Emergent Adverse Events by MedDRA Preferred Term in Decreasing Order of Frequency by Age Group From Baseline to Week 52	Safety
3.2.9.3	Summary of Serious Treatment-Emergent Adverse Events by MedDRA Preferred Term in Decreasing Order of Frequency in LTS Period	Safety
3.2.10.1	Summary of Treatment-Related Treatment-Emergent Adverse Events by MedDRA System Organ Class and Preferred Term in VC Period	Safety
3.2.10.1.1	Summary of Treatment-Related Treatment-Emergent Adverse Events by MedDRA System Organ Class and Preferred Term by Age Group in VC Period	Safety

Table No.	Title	Population
3.2.10.2	Summary of Treatment-Related Treatment-Emergent Adverse Events by MedDRA System Organ Class and Preferred Term From Baseline to Week 52	Safety
3.2.10.2.1	Summary of Treatment-Related Treatment-Emergent Adverse Events by MedDRA System Organ Class and Preferred Term by Age Group From Baseline to Week 52	Safety
3.2.10.3	Summary of Treatment-Related Treatment-Emergent Adverse Events by MedDRA System Organ Class and Preferred Term in LTS Period	Safety
3.2.11.1	Summary of Treatment-Related Treatment-Emergent Adverse Events by MedDRA Preferred Term in Decreasing Order of Frequency in VC Period	Safety
3.2.11.1.1	Summary of Treatment-Related Treatment-Emergent Adverse Events by MedDRA Preferred Term in Decreasing Order of Frequency by Age Group in VC Period	Safety
3.2.11.2	Summary of Treatment-Related Treatment-Emergent Adverse Events by MedDRA Preferred Term in Decreasing Order of Frequency From Baseline to Week 52	Safety
3.2.11.2.1	Summary of Treatment-Related Treatment-Emergent Adverse Events by MedDRA Preferred Term in Decreasing Order of Frequency by Age Group From Baseline to Week 52	Safety
3.2.11.3	Summary of Treatment-Related Treatment-Emergent Adverse Events by MedDRA Preferred Term in Decreasing Order of Frequency in LTS Period	Safety
3.2.14.1	Summary of Grade 3 or Higher Treatment-Related Treatment-Emergent Adverse Events by MedDRA System Organ Class and Preferred Term in VC Period	Safety
3.2.14.1.1	Summary of Grade 3 or Higher Treatment-Related Treatment-Emergent Adverse Events by MedDRA System Organ Class and Preferred Term by Age Group in VC Period	Safety
3.2.14.2	Summary of Grade 3 or Higher Treatment-Related Treatment-Emergent Adverse Events by MedDRA System Organ Class and Preferred Term From Baseline to Week 52	Safety
3.2.14.2.1	Summary of Grade 3 or Higher Treatment-Related Treatment-Emergent Adverse Events by MedDRA System Organ Class and Preferred Term by Age Group From Baseline to Week 52	Safety
3.2.14.3	Summary of Grade 3 or Higher Treatment-Related Treatment-Emergent Adverse Events by MedDRA System Organ Class and Preferred Term in LTS Period	Safety
3.2.15.1	Summary of Treatment-Related Serious Treatment-Emergent Adverse Events by MedDRA System Organ Class and Preferred Term in VC Period	Safety
3.2.15.1.1	Summary of Treatment-Related Serious Treatment-Emergent Adverse Events by MedDRA System Organ Class and Preferred Term by Age Group in VC Period	Safety
3.2.15.2	Summary of Treatment-Related Serious Treatment-Emergent Adverse Events by MedDRA System Organ Class and Preferred Term From Baseline to Week 52	Safety
3.2.15.2.1	Summary of Treatment-Related Serious Treatment-Emergent Adverse Events by MedDRA System Organ Class and Preferred Term by Age Group From Baseline to Week 52	Safety
3.2.15.3	Summary of Treatment-Related Serious Treatment-Emergent Adverse Events by MedDRA System Organ Class and Preferred Term in LTS Period	Safety
3.2.16.1	Summary of Treatment-Emergent Adverse Events With a Fatal Outcome by MedDRA System Organ Class and Preferred Term in VC Period	Safety

Table No.	Title	Population
3.2.16.1.1	Summary of Treatment-Emergent Adverse Events With a Fatal Outcome by MedDRA System Organ Class and Preferred Term by Age Group in VC Period	Safety
3.2.16.2	Summary of Treatment-Emergent Adverse Events With a Fatal Outcome by MedDRA System Organ Class and Preferred Term From Baseline to Week 52	Safety
3.2.16.2.1	Summary of Treatment-Emergent Adverse Events With a Fatal Outcome by MedDRA System Organ Class and Preferred Term by Age Group From Baseline to Week 52	Safety
3.2.16.3	Summary of Treatment-Emergent Adverse Events With a Fatal Outcome by MedDRA System Organ Class and Preferred Term in LTS Period	Safety
3.2.19.1	Summary of Treatment-Emergent Adverse Events Leading to Dose Interruption by MedDRA System Organ Class and Preferred Term in VC Period	Safety
3.2.19.1.1	Summary of Treatment-Emergent Adverse Events Leading to Dose Interruption by MedDRA System Organ Class and Preferred Term by Age Group in VC Period	Safety
3.2.19.2	Summary of Treatment-Emergent Adverse Events Leading to Dose Interruption by MedDRA System Organ Class and Preferred Term From Baseline to Week 52	Safety
3.2.19.2.1	Summary of Treatment-Emergent Adverse Events Leading to Dose Interruption by MedDRA System Organ Class and Preferred Term by Age Group From Baseline to Week 52	Safety
3.2.19.3	Summary of Treatment-Emergent Adverse Events Leading to Dose Interruption by MedDRA System Organ Class and Preferred Term in LTS Period	Safety
3.2.20.1	Summary of Treatment-Emergent Adverse Events Leading to Discontinuation of Study Drug by MedDRA System Organ Class and Preferred Term in VC Period	Safety
3.2.20.1.1	Summary of Treatment-Emergent Adverse Events Leading to Discontinuation of Study Drug by MedDRA System Organ Class and Preferred Term by Age Group in VC Period	Safety
3.2.20.2	Summary of Treatment-Emergent Adverse Events Leading to Discontinuation of Study Drug by MedDRA System Organ Class and Preferred Term From Baseline to Week 52	Safety
3.2.20.2.1	Summary of Treatment-Emergent Adverse Events Leading to Discontinuation of Study Drug by MedDRA System Organ Class and Preferred Term by Age Group From Baseline to Week 52	Safety
3.2.20.3	Summary of Treatment-Emergent Adverse Events Leading to Discontinuation of Study Drug by MedDRA System Organ Class and Preferred Term in LTS Period	Safety
3.2.21.1	Summary of Treatment-Emergent Adverse Events Requiring Concomitant Medications by MedDRA System Organ Class and Preferred Term in VC Period	Safety
3.2.21.1.1	Summary of Treatment-Emergent Adverse Events Requiring Concomitant Medications by MedDRA System Organ Class and Preferred Term by Age Group in VC Period	Safety
3.2.21.2	Summary of Treatment-Emergent Adverse Events Requiring Concomitant Medications by MedDRA System Organ Class and Preferred Term From Baseline to Week 52	Safety
3.2.21.2.1	Summary of Treatment-Emergent Adverse Events Requiring Concomitant Medications by MedDRA System Organ Class and Preferred Term by Age Group From Baseline to Week 52	Safety

Table No.	Title	Population
3.2.21.3	Summary of Treatment-Emergent Adverse Events Requiring Concomitant Medications by MedDRA System Organ Class and Preferred Term in LTS Period	Safety
Laboratory		
3.3.1.1	Summary of Laboratory Values – Hematology From Baseline to Week 52	Safety
